5.3 DRUG CONCENTRATION MEASUREMENTS AND PHARMACOKINETICS

5.3.1 Assessment of pharmacokinetics

[figure not shown]
If data allow, the PK parameters of BI 905681 mentioned as secondary endpoints will be evaluated using non-compartmental analysis (NCA) methods according to the current BI internal and [REDACTED] Standard Operation Procedures (SOPs).

Pharmacokinetic data may additionally be analysed using a population pharmacokinetic approach. Modelling and simulation activities will be planned and documented separately according to internal and external guidelines and SOPs.

5.3.2 Methods of sample collection

For quantification of analyte serum concentrations, samples will be drawn at the time points listed in the respective Flow Charts ([Schedule A](#), [Table 10.2:1](#) and [Schedule B](#), [Table 10.2:2](#)).

If collected from an arm, it is essential to collect blood from the arm that is opposite to the arm used for infusion in order to avoid artificially high or low drug concentration determinations. Further details on sample characteristics, processing, handling, and shipment are provided in the Laboratory Manual. After completion of the trial, serum samples may be used for further methodological investigations, e.g. stability testing. However, only data related to the analyte or bioanalytical assay will be generated by these additional investigations. The trial samples will be discarded after completion of the additional investigations but not later than 5 years after the final trial report has been signed.

5.3.4 Pharmacokinetic – pharmacodynamic relationship

No formal analysis of a PK/PDc relationship is planned.

Correlation between drug concentration and response may be made if adequate data are available. In addition, exploratory correlation may also be made between drug concentration and AEs.

Data may also be used to develop PK-PDc models, if feasible. Modelling and simulation activities will be planned and documented separately according to internal and external guidelines and SOPs.

5.4 ASSESSMENT OF BIOMARKER(S)

The evaluation of several biomarkers will be performed in an exploratory manner as a means of identifying whether, for example, pharmacodynamics modulation is achieved during the dose escalation part of the trial. Where consent is given, tumour samples will be obtained as detailed below. Tumor sampling must only be performed for patients who have undergone screening assessments, have a historically confirmed RNF43 mutation or R-spondin fusion, and are expected to be eligible for treatment in the trial. The following exploratory biomarkers are planned to be examined in tumor biopsies attained during the trial:

- Pharmacodynamics modulation of genes associated with Wnt signaling including but not limited to *AXIN2* mRNA expression.
- Tumour microenvironment changes induced by BI 905681 intervention, as determined by an analysis of an immune-oncology-related panel of genes.
- β -catenin staining pattern using immunohistochemistry.
- Genomic profiling of tumour samples implementing next generation sequencing.
- Immune oncology related targets including but not limited to CD8 and PDL1.

The aforementioned analysis will be undertaken should enough formalin-fixed and paraffin-embedded (FFPE) material be available. All samples are expected to be exhausted during the course of investigative analysis. Should this not be the case, samples might also be used for assay validation and concordance testing. Until then, samples will be stored at Boehringer Ingelheim or [REDACTED].

5.4.1 Methods of sample collection

Biopsies should be taken according to the [Flow Chart](#). Pre- and on-treatment tumour biopsy (where feasible, from the same lesion) collections for biomarker analyses will be mandatory from all patients who have a historically confirmed RNF43 mutation or R-spondin fusion entering the trial starting from Cohort 2. Where mandatory, an archival sample (25 x 4-5 μ m-sections), from the most recent relapse, will be acceptable as the pre-treatment biopsy, if taken within 6 months of trial start. Otherwise a pre-treatment fresh tumour biopsy must be taken and formalin fixed paraffin embedded (FFPE) and stored at room temperature. On-treatment samples must also be FFPE and stored at room temperature until shipped. Detailed instructions for sampling, handling, and shipment of samples are provided in the laboratory manual, but in short:

Proprietary confidential information © 2019 Boehringer Ingelheim International GmbH or one or more of its affiliated companies

- For a fresh baseline sample a minimum of 2 core needle biopsies or 1 punch biopsy must be taken between screening and the day before first treatment with BI 905681. An archival sample, from the most recent relapse, will be acceptable as the pre-treatment biopsy (25 x 4-5µm-sections), if taken within 6 months of trial start.
- Two core-needle biopsies (preferably from the same lesion) 24 hours after Cycle 2 infusion (the on-treatment biopsy time point may be adapted based on PK analysis).

All samples must be adequately labelled by the trial site personnel. Details about tumour tissue, labelling of tubes, storage, and shipment (frequency and addresses) will be provided in the laboratory manual.

As medical knowledge in this field is constantly evolving, other tissue/blood biomarkers that may become relevant as predictive markers of treatment response may also be explored via available tissues/blood or acquisition of additional tumour tissues/blood. The list of biomarkers planned to be studied during the trial may change based on new information in the literature or early analyses.

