- d Safety laboratory tests and urinalysis at follow-up are optional and at the discretion of the investigator.
- e Vitamin D will be tested at Screening, on Day 1 of every third cycle (i.e. Cycle 3 Day 1, Cycle 6 Day 1) and at the EOT.
- f Pregnancy test is only required for women of childbearing potential.
- g Bone densitometry at the EOT visit is not required if bone densitometry has been performed within the previous 4 weeks.
- h Ophthalmologic assessment will be performed for all patients at Screening visit and if the patient develops visual symptoms during the trial. The following assessments should be performed: BCVA, colour fundus photography, and spectral domain optical coherence tomography (SD-OCT) (see [Section 5.2.5.4](#)).
- i Tumour assessments performed prior to informed consent as part of routine clinical practice will be accepted if they meet the requirements of the protocol and are performed within the Screening visit window. Tumour assessment should be performed every 6 weeks calculated from start of treatment until documented progression. In the event of early discontinuation or an interruption/delay to treatment, wherever possible the tumour assessment schedule should not be changed.
- j Pre- and on-treatment tumour biopsy collections for biomarker analyses are mandatory from all patients who have a historically confirmed RNF43 mutation or R-spondin fusion entering the trial from Cohort 2 A total of 2 tumour biopsies are required. The first tumour biopsy may be obtained any time prior to the first dose. For a fresh baseline sample a minimum of 2 core needle biopsies or 1 punch biopsy must be taken between Screening and the day before first treatment with BI 905681. An archival sample, from the most recent relapse, will be acceptable as the pre-treatment biopsy, if taken within 6 months of trial start. A second tumour biopsy sample (two core-needle biopsies or 1 punch biopsy, preferably from the same

Proprietary confidential information © 2019 Boehringer Ingelheim International GmbH or one or more of its affiliated companies

lesion) will be obtained 24 hours after Cycle 2 infusion (the on-treatment biopsy time point may be adapted based on PK analysis). See [Section 5.4.1](#).

- k Bone biomarkers will be assessed on Cycle 1 Day 1, Cycle 2 Day 1 and then on Day 1 of every odd-numbered cycle and the EOT visit.
- l For detailed schedule, refer to [Appendix 10.2](#).

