3.3.3 Exclusion criteria

1. Major surgery (major according to the investigator's assessment) performed within 4 weeks prior to first trial treatment or planned within 6 months after Screening
2. Previous or concomitant malignancies other than the one treated in this trial within the last 2 years, except:
 - a) effectively treated non-melanoma skin cancers
 - b) effectively treated carcinoma in situ of the cervix
 - c) effectively treated ductal carcinoma in situ

² A woman is considered of childbearing potential (WOCBP), i.e. fertile, following menarche and until becoming post-menopausal unless permanently sterile.

Permanent sterilisation methods include hysterectomy, bilateral salpingectomy and bilateral oophorectomy.

Tubal ligation is NOT a method of permanent sterilisation.

A postmenopausal state is defined as no menses for 12 months without an alternative medical cause.

Proprietary confidential information © 2019 Boehringer Ingelheim International GmbH or one or more of its affiliated companies

- d) other effectively treated malignancy that is considered cured by local treatment
- 3. Osteoporosis \geq CTCAE Grade 2
- 4. Chronic corticosteroid use, except as permitted for the maintenance therapy of brain metastases (see Exclusion Criterion 13)
- 5. Osteoporotic compression fracture within 12 months prior to informed consent which is clinically significant in the opinion of the investigator.
- 6. Patient who must or wishes to continue the intake of restricted medications or any drug considered likely to interfere with the safe conduct of the trial.
- 7. Previous treatment in this trial.
- 8. Treatment with a systemic anti-cancer therapy or investigational drug within 28 days or 5 half-lives (whichever is shorter) of the first treatment with the study medication.
- 9. Any history of or concomitant condition that, in the opinion of the investigator, would compromise the patient's ability to comply with the study or interfere with the evaluation of the safety and efficacy of the test drug.
- 10. Women who are pregnant, nursing, or who plan to become pregnant or nurse during the trial or within 6 months after the last dose of study treatment.
- 11. Active alcohol or drug abuse in the opinion of the investigator.
- 12. Patient unwilling or unable to comply with the protocol.

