8.6 TRIAL MILESTONES

The **start of the trial** is defined as the date when the first patient in the whole trial signs informed consent.

The end of the trial is defined as the date of the last visit of the last patient in the whole trial (“Last Patient Out”).

The “**Last Patient Drug Discontinuation**” (LPDD) date is defined as the date on which the last patient at an individual trial site ends trial medication (as scheduled per protocol or prematurely). Individual investigators will be notified of Suspected Unexpected Serious Adverse Reactions (SUSARs) occurring with the trial medication until 30 days after LPDD at their site.

Early termination of the trial is defined as the premature termination of the trial due to any reason before the end of the trial as specified in this protocol.

Temporary halt of the trial is defined as any unplanned interruption of the trial by the sponsor with the intention to resume it.

Suspension of the trial is defined as an interruption of the trial based on a Health Authority request.

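### The 6-month window for archival baseline tissue runs from the trial's start date, not the patient's first dose, so for later patients it admits older archival samples and can reject recent ones

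*Protocol*

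**What the plan says.** Tumour biopsies before and on treatment are mandatory, from Cohort 2 onwards, for patients with a known RNF43 mutation or R-spondin fusion (Protocol Section 5.4.1). Two routes lead to the baseline sample.

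- **Archival.** Footnote j of the Schedule A and Schedule B flow charts states: "An archival sample, from the most recent relapse, will be acceptable as the pre-treatment biopsy, if taken within 6 months of trial start". Section 5.4.1 gives the same condition twice: such a sample "will be acceptable as the pre-treatment biopsy, if taken within 6 months of trial start". So the phrase "if taken within 6 months of trial start" stands in four places.
- **Fresh.** If no archival sample qualifies, Section 5.4.1 adds: "Otherwise a pre-treatment fresh tumour biopsy must be taken". That sample "must be taken between screening and the day before first treatment with BI 905681".

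Section 8.6 (Trial milestones) says that the start of the trial "is defined as the date when the first patient in the whole trial signs informed consent". The documents contain no other definition. Footnote j also says, without a lower limit, that the first biopsy may be obtained at any point before the first dose.

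**The concern.** The archival window is tied to one calendar date shared by everyone, while the patients it governs enter later, each at a different distance from that date. Nearby timing rules follow the patient. The fresh biopsy ends the day before that patient's first treatment. The washout in exclusion criterion 8 (Section 3.3.3) is "within 28 days or 5 half-lives (whichever is shorter) of the first treatment with the study medication". Baseline imaging (Section 5.1) is counted back from treatment, and the SAP (Section 6.7) defines baseline as the time point closest to and before first administration.

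The baseline sample is the reference for the on-treatment change in AXIN2 and other Wnt-related genes. Section 3.1 has back-filled patients recruited so that exposure can be correlated with pharmacodynamic effect, and lists pharmacodynamics among the SMC's inputs to dose decisions. Section 4.1.7 brings target-engagement data into the choice of expansion doses. Section 5.2 allows biomarker data to inform the recommended Phase 2 dose when DLTs are few. Older tissue adds elapsed time, and possibly intervening treatment, to whatever change the drug causes. Numbers are small: Section 3.1 aims for at least 2 such patients per cohort, so at that minimum one unsuitable baseline is half of a dose level's pairs. Rejecting recent archival tissue also means an invasive biopsy that a patient-level window would avoid.

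**Working it through.** The plan gives no figure of its own here, so the check is date arithmetic.

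**Inputs**
- Window: 6 months, direction not stated (Section 5.4.1; footnote j).
- Anchor: the first consent in the trial (Section 8.6), taken as month 0.
- t: months from month 0 to the patient's first dose. This is an assumption, shown as a range.

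**Formulas** (age of the archival sample at first dose)
- Oldest that qualifies: t + 6.
- Youngest that qualifies, window both ways: max(0, t − 6).
- Youngest that qualifies, window backwards only: t.

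| t (assumed) | Oldest | Youngest, both ways | Youngest, backwards only |
|---|---|---|---|
| 1 | 7 | 0 | 1 |
| 3 | 9 | 0 | 3 |
| 6 | 12 | 0 | 6 |
| 12 | 18 | 6 | 12 |
| 18 | 24 | 12 | 18 |
| 24 | 30 | 18 | 24 |

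**Example, t = 12.** Tissue taken 2 months before the first dose dates from month 10. A two-way window closed at month 6 and a backward-only window at month 0, so this sample is rejected either way. Tissue taken at month −6 is 18 months old and is accepted if it comes from the most recent relapse.

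**Smallest plausible effect.** Take the fastest pace the protocol allows in Schedule A: cohorts of 2, patients 72 hours apart, then a 21-day DLT period (Sections 3.1 and 7.3.1). That is 3 + 21 = 24 days per cohort. With 30.44 days to a month:
- Cohort 2 starts 24 days (0.8 month) after the first dose in the trial. Oldest qualifying sample: at least 6.8 months.
- Cohort 5 starts 4 × 24 = 96 days (3.2 months) after it. Oldest: at least 9.2 months.

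These are lower bounds, because month 0 is the first consent, which precedes the first dose. So the oldest qualifying sample exceeds 6 months for every patient concerned. Rejection of recent archival tissue under a two-way window needs t > 6, which this pace does not reach in Schedule A.

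**With a patient-level anchor.** If the window is the 6 months before the patient's own first dose, the oldest qualifying sample is 6 months old whatever t is, and recent tissue is always inside.

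**The case against.** **Intended meaning.** The biopsy text does not cite Section 8.6, and its neighbouring rules are per patient, so a patient-level start was probably meant. A laboratory manual, not available here, holds the detailed instructions. This is a fair reason to call the problem one of wording. It does not remove it, since the only definition in the documents is trial-level and all four places use the phrase.

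**Fresh tissue.** A reader might infer that fresh tissue fails to qualify for later patients. It does not: the fresh route is tied to the patient and open to all. Only recent archival tissue can be shut out.

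**Earlier therapy.** A reader might infer that old archival samples will usually predate the therapy the patient then failed. The sample must be "from the most recent relapse, will be acceptable as the pre-treatment biopsy", which limits this, and progression on that therapy could itself be read as the latest relapse. The documents give no frequency. What stands is that intervening therapy is not excluded.

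**Reach.** A reader might carry the problem through the optimal biological dose into the primary endpoint. The tumour biomarkers are exploratory (Section 5.4), no formal PK/PDc analysis is planned (Section 5.3.4), and no passage makes paired AXIN2 change a criterion for that dose. The BLRM uses DLTs only.

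**Elapsed time.** The protocol version (15 November 2019) and the SAP (17 January 2022) are about 26 months apart, but neither date is a first consent or a first dose, so that gap is not an accrual time. Schedule B, where t would have been largest, never opened (SAP Sections 4 and 6.1).

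**Conclusion.** The point holds as a wording error with a modest consequence. Followed as written, the rule admits archival tissue up to t + 6 months old and can turn away recent archival tissue. The excess over 6 months equals t, so it is at least about 0.8 to 3.2 months for Cohorts 2 to 5 and grows with slower accrual. The values at t = 6 and above rest on assumed accrual times, and rejection of recent tissue depends also on which direction the window is meant to run. The most-recent-relapse condition limits how many old samples would qualify in practice; the documents do not allow that number to be estimated.

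What is affected is the baseline of an exploratory paired readout that the SMC may weigh alongside other data. The model-based MTD does not depend on it. The correction should be made because it is nearly free and the pairs are few.

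**What to change.** In all four places (twice in Section 5.4.1, and in footnote j of both flow charts), replace the reference to trial start with *within 6 months before the patient's first dose of BI 905681*. This sets both the anchor and the direction. In footnote j, reconcile the sentence that lets the first biopsy be obtained at any point before the first dose with this window and with the fresh-biopsy window.

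For each biopsy pair, report the age of the baseline sample at first dose and any anti-cancer therapy given between the sample and that dose. Section 6.2.1.3 already collects start and end dates of prior therapy. Pharmacodynamic pairs can then be shown with and without older samples or samples with intervening therapy. A ban on intervening therapy should not be added: it would be a new requirement and would force more fresh biopsies.

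The trial ended early with only Schedule A investigated, so the reporting step is the useful one for data in hand; the wording change serves any amendment or later protocol built on this text. The cost is one phrase in four places and a listing. The small downside is that a few patients with older archival tissue would need the fresh biopsy the protocol already provides for.

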5.5 OTHER ASSESSMENTS

5.5.1 ADA assessments

For ADA assessment, samples will be drawn at the time points listed in the respective Flow Charts ([Schedule A, Table 10.2:1](#) and [Schedule B, Table 10.2:2](#)).

Details on sample collection, characteristics, processing, handling, and shipment are provided in the Laboratory Manual. The trial samples will be discarded after completion of the additional investigations but not later than 5 years after the final trial report has been signed.

Note that for some disease indications, it may be necessary to use serum samples collected prior to administration of test article in order to assess the performance of the ADA assay. Such use of pre-dose samples will not compromise the collection of valid ADA data for those pre-dose samples.

[REDACTED]

[REDACTED]

[REDACTED]

[REDACTED]

5.6 APPROPRIATENESS OF MEASUREMENTS

All assessments have been planned in accordance with traditional oncology Phase I trial methodology.

6. INVESTIGATIONAL PLAN

6.1 VISIT SCHEDULE

Patients meeting the inclusion and exclusion criteria for the part they are participating in and who have signed a written ICF, are eligible for participation in the trial. Patients will visit the clinical site at the time points specified in [Schedule A Flow Chart](#) and [Schedule B Flow Chart](#) specific to each part. If a patient misses a scheduled visit, and reports to the Investigator between the missed visit and the next scheduled visit, the assessments for the missed visit must be done with the actual date and the reason must be given for the delayed visit. The next visit must then take place at the scheduled time after the first administration of the trial drug in the respective treatment cycle.

Once the decision is made for any reason for a patient to stop the treatment with BI 905681, an EOT visit must occur as soon as possible (no later than 7 days after stopping treatment). After the EOT visit, the patient must undergo a follow-up safety evaluation 42 (+7) days after the last administration of trial therapy.

The trial will be conducted according to the principles of GCP.

6.2 DETAILS OF TRIAL PROCEDURES AT SELECTED VISITS

The procedures required at each trial visit in both portions of the trial are presented in [Schedule A Flow Chart](#) and [Schedule B Flow Chart](#) of this protocol. The key procedures required include:

- PK samples throughout the trial
- Reporting of all AEs occurring after the ICF has been signed
- Baseline and on-treatment blood biomarker and immunogenicity assessments
- Tumour biopsy biomarker assessments
- Tumour assessments (based on computed tomography [CT] / positron emission tomography [PET] and/or magnetic resonance imaging [MRI] scan) according to RECIST Version 1.1 must be performed once every 2 cycles (meaning every 6 weeks for Schedule A and every 8 weeks for [Schedule B](#) if there are no delays in cycles but as close as possible to the end of the second of the 2 cycles of treatment if there was a delay) after the start of BI 905681.

6.2.1 Screening and run-in period(s)

6.2.1.1 Screening Period

The Screening period may run over a period of 28 days (period within the trial and before the first intake of BI 905681). For the detailed description of the tests to be performed during this period and their timing, please refer to [Schedule A Flow Chart](#) and [Schedule B Flow Chart](#).

6.2.1.2 Baseline Conditions

Demographics (sex, birth date, race, and ethnicity where allowed), information on tobacco and alcohol use, and baseline conditions will be collected during the Screening visit.

6.2.1.3 Medical History

History of the patient's cancer will be obtained. The type of cancer, the date of the first histological diagnosis (month and year may be sufficient), and the primary tumour site will be reported on the eCRF. The differentiation grade (not specified, undifferentiated, poorly differentiated, moderately differentiated, well differentiated) obtained at the time of diagnosis and the location of metastatic sites as well as the stage according to the tumour, (lymph) node, metastasis (TNM) classification will be provided as obtained at diagnosis and at trial screening. Previous surgeries will be reported.

Previously administered chemotherapy, vaccine therapy, antibodies therapy, kanamycin or similar class drugs (including streptomycin, gentamicin, amikacin, tobramycin and neomycin), immune therapy, and hormone therapy will be reported, including start and end dates (month and year may be sufficient), as well as whether therapy was given as neoadjuvant, adjuvant, or palliative therapy. The date of tumour progression after previous line of treatment will be recorded, if known.

